**Objectives:**

To assess the efficacy and effects of prone positioning on the respiratory physiology and death rate of patients suffering from covid pneumonia/ acute respiratory distress syndrome.

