**Research Questions:**

Does prone positioning increase the oxygen saturation of blood?

Does prone positioning have any effect on the severity of illness- if prone positioning has any benefits in terms of decreased severity of illness or in terms of decreased mortality at 3 months in patients with covid pneumonia?

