**Study Protocols:**

All the patients who are received in the medical emergency department as a suspected case of covid pneumonia/ acute respiratory distress syndrome (ARDS), will be assessed in the emergency department as per hospital protocols. If admitted for covid pneumonia/ ARDS, the patient will be offered to consent for participation in the study. The patients who themselves cannot consent due to severity of condition, the attendant closest in relation to the patient will be asked about the consent.

Patient will then be randomized through permuted block randomization into either a control or experimental group and shifted to the respective ward.

Complete data will be recorded on the questionnaire and will be considered as the day one of admission of the patient.

Patients in the prone position group will then be guided for prone positioning for eight hours of intermittent prone positioning. Each cycle may be from 30 minutes to 3 hours. Prone positioning was to be done under the supervision of the staff who were trained by the researchers. The prone positioning was to be done by patient him/herself after guidance with assistance if required so that patient is more comfortable.

Researcher will visit each patient twice a day to ensure if the patient was properly getting the prone positioning intervention and to assess if the patient can tolerate it. In case any complication happens due to the manoeuvre, it will be discussed with the lead investigator. The patient will be assessed for fitness to continue being part of the study or to withdraw from the study.

Record of the prone positioning cycles will be maintained by the staff in the patient file.

Seventh day will be the last day of prone positioning. Data will be recorded by the researcher on seventh day of admission at least ten minutes after the patient has been put to supine position.

Data will also be collected at 14th day of admission of the patient, if the patient is still in the ward.

Patient survival at 90th day will be confirmed by calling the patient/ attendant and requesting for death certificate in case the patient died after discharge from the facility.

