**Analyses:** Data will be analysed on SPSS version 25. Statistical tests will be applied to see effect of prone positioning on the severity of covid pneumonia and acute respiratory distress syndrome and to find out its effects on mortality and respiratory physiology – PaO2, respiratory rate and oxygen requirement as determined by the type of oxygen delivery mask, with a confidence interval of 95%. P value of <0.05 will be considered statistically significant. Data will be presented in tables, bar charts, and pie diagrams. Tests of significance will be applied to see effects of prone positioning on respiratory physiology and Kaplan Meier curve will be obtained to compare the survival of the two groups.

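### Five outcomes share one unadjusted p<0.05 rule and none is ranked, so the chance of at least one false positive is about 10% to 23%, not 5%

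*Combined protocol and SAP*

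**What the plan says.** The Objectives section puts physiology and death on an equal footing: "To assess the efficacy and effects of prone positioning on the respiratory physiology and death rate of patients". The Research Questions ask three things without ranking them: oxygen saturation ("Does prone positioning increase the oxygen saturation of blood"), severity of illness, and survival ("in terms of decreased mortality at 3 months in patients with covid pneumonia").

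The Analyses section lists what will be tested: severity of disease first, then "to find out its effects on mortality and respiratory physiology". It spells out physiology as PaO2, "respiratory rate and oxygen requirement as determined by the type of oxygen delivery mask". That makes five named outcomes. The only decision criterion is "P value of <0.05 will be considered statistically significant", alongside 95% confidence intervals. A Kaplan-Meier comparison of survival is planned, but no test for it is named.

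On timing, Study Protocols fixes survival at day 90. For the other measures it says "Data will be recorded by the researcher on seventh day of admission at least ten minutes after" the return to supine, with a further collection on the 14th "day of admission of the patient, if the patient is still in the ward". Analyses does not say which day the arms are compared on.

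No outcome is called primary, secondary or exploratory from Objectives through Analyses, and no multiplicity adjustment is mentioned. The pages before Objectives were not available for review.

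**The concern.** A 5% threshold limits the false-positive risk of one test. Applied separately to five outcomes, it does not limit the risk that at least one of them is wrongly called significant.

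The five outcomes also differ greatly in meaning. A day-7 difference in respiratory rate and a day-90 difference in survival would earn the same label under the same rule. With no outcome designated in advance as the main one, whichever crosses 0.05 can become the headline, and a reader cannot tell a planned main result from one of several that happened to succeed.

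**Working it through.** The plan states no family-wise error rate, sample size, power or event rate. The only figure of its own to start from is the per-test threshold of 0.05.

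**Inputs from the document**
- Threshold 0.05, unadjusted (Analyses).
- Two arms, hence one comparison per outcome (Study Protocols).
- k = 5 outcomes: severity, mortality, PaO2, respiratory rate, oxygen requirement (Analyses).

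**Assumptions, not in the document**
- No true effect on any outcome.
- One test per outcome, two-sided. Sidedness is not stated; two-sided fits the 95% confidence interval.
- Jointly normal test statistics with the same correlation ρ between every pair, shown at 0, 0.5, 0.8 and 0.9.

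**Independent tests**
- Either direction: 1 − 0.95^5 = 0.226.
- False benefit only (each test at 0.025 in the favourable direction): 1 − 0.975^5 = 0.119.

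**Correlated tests**

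Each statistic is written as √ρ·U + √(1−ρ)·E, with U shared and E separate, both standard normal. With c = 1.96, φ the standard normal density and Φ its distribution function:

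- Either direction: 1 − ∫ φ(u) [Φ((c − √ρ u)/√(1−ρ)) − Φ((−c − √ρ u)/√(1−ρ))]^k du
- Benefit only: 1 − ∫ φ(u) [Φ((c − √ρ u)/√(1−ρ))]^k du

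| Tests | Error counted | ρ=0 | ρ=0.5 | ρ=0.8 | ρ=0.9 |
|---|---|---|---|---|---|
| 5 | either direction | 22.6% | 18.3% | 12.7% | 10.2% |
| 5 | false benefit | 11.9% | 9.1% | 6.4% | 5.1% |
| 4 | either direction | 18.5% | 15.6% | 11.4% | 9.4% |
| 6 | either direction | 26.5% | 20.7% | 13.9% | 10.8% |

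The reference values for one test are 5% in either direction and 2.5% for benefit. A simulation of 10 million draws at ρ = 0.9 gave 10.15% for five tests in either direction, in agreement with the integral.

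The four-test row is what remains if a primary outcome is named in the pages not seen. The six-test row applies if oxygen saturation, which is a research question but is not in the Analyses list, is tested separately from PaO2. Splitting severity into pneumonia and ARDS, or testing on both day 7 and day 14, would add further tests.

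**Error under the remedies, same assumptions**
- One primary outcome tested at 0.05, no significance claims for the rest: 5.0% at any ρ.
- Holm across five: with no true effects, Holm rejects something only if the smallest p is at or below 0.05/5 = 0.01. At ρ = 0 the error is 1 − 0.99^5 = 4.9%; at ρ = 0.5, 0.8 and 0.9 it is 4.2%, 3.0% and 2.3%.
- Holm across six: 4.9%, 4.1%, 2.8% and 2.1%.

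**The case against.** The strongest objection is that a primary outcome may be named in the pages not seen. Its error would then stay at 5%, and unadjusted p-values on secondary outcomes would be a familiar reporting choice. This stands as a limit on the point: the five-outcome figure would no longer describe the main claim. The Analyses rule would still let the other four be called significant without adjustment or an exploratory label.

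A second objection is that the plan never says one success in five establishes efficacy. It only defines when a p-value is called significant, and a reader shown all five results could allow for multiplicity. That is fair as far as it goes. But the plan has no other criterion for a positive result, so nothing in the visible text prevents an any-of-five claim.

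Third, the research questions are directional, so false benefit is the error most likely to mislead practice, and it is about half the either-direction figure. This is right, and both are shown. Relative to its own reference, false benefit is inflated to a similar degree: 11.9/2.5 = 4.8 times when independent and 5.1/2.5 = 2.0 times at ρ = 0.9.

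Fourth, physiology could count as one domain, leaving three tests: 14.3% when independent and 8.4% at ρ = 0.9, with false benefit at 7.3% and 4.2%. The Analyses section lists the three measures separately and plans no composite, so five is the better reading. Even three tests exceed the nominal level.

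Finally, the normal, equal-correlation model is generic, and mask type and death are not continuous. The correlated figures are therefore indicative rather than exact.

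**Conclusion.** The concern holds. As written, the significance rule allows any of five unranked outcomes to be called significant, with a chance of at least one false positive of 22.6% when independent, falling to 10.2% at a common correlation of 0.9. That is about 4.5 to 2.0 times the nominal 5%. These figures rest on no true effects, one two-sided test per outcome and the assumed correlations.

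The rule should be changed. Confidence is moderate rather than high, only because a primary outcome might be named in the unseen pages.

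**What to change.** Before any comparison by arm, add to Analyses:

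1. **One primary outcome at one time point**, tested alone at two-sided 0.05. The choice is the sponsor's. Death by day 90 is one candidate, because its follow-up is not limited to patients still in the ward. If it is chosen, state whether the test compares day-90 proportions or time to death, since the planned Kaplan-Meier curve does not settle this.
2. **All other outcomes exploratory**, reported as estimates with 95% confidence intervals and no significance claims. Report day 14 descriptively.
3. **If the sponsor will not rank the outcomes**, Holm's procedure across the five, with mortality at day 90 and the other four at day 7. The ordered p-values are compared with 0.05/5 = 0.01, 0.05/4 = 0.0125, 0.05/3 = 0.0167, 0.05/2 = 0.025 and 0.05, stopping at the first failure.
4. **Oxygen saturation**, if analysed separately from PaO2: either add it to the Holm family, which then starts at 0.05/6 = 0.0083, or label it exploratory.

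The change takes a few sentences and no new data. With a single primary, no other outcome can be called significant. With Holm, an isolated p-value between about 0.01 and 0.05 no longer qualifies. A day-90 death primary may have limited power; the visible text gives no sample size or event rate with which to judge this. Any confirmatory day-7 test, including those in the Holm option, also needs a stated analysis rule for patients who died or were discharged before day 7. Neither Study Protocols nor Analyses gives one, and multiplicity control does not replace it.
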